### 10.2. Populations for Analyses

#### 10.2.1. Study Participant Disposition

All subjects who discontinue from the study will be identified and the extent of their participation in the study will be reported. If known, a reason for their discontinuation will be recorded.

A detailed description of subject disposition will be provided at the end of the study.

### **10.2.2. Study Participant Characteristics**

The subject's age, sex, race, weight, BMI, height, smoking habits, or other demographic characteristics will be recorded and may be used in the PK, PD, and safety analyses as quantitative or classification variables.

## **10.3. Statistical Analyses**

Statistical analysis of this study will be the responsibility of Lilly or its designee.

PK/PD analyses will be performed on the full analysis set. This set includes all data from all randomized subjects receiving at least 1 dose of the investigational product according to the treatment the subjects actually received. Safety analyses will be performed for all enrolled subjects, whether or not they completed all protocol requirements.

Additional exploratory analyses of the data will be performed as deemed appropriate. Study results may be pooled with the results of other studies for population PK analysis purposes to avoid issues with post hoc analyses and incomplete disclosures of analyses.

### **10.3.1. Safety Analyses**

#### **10.3.1.1. Clinical Evaluation of Safety**

All investigational product and protocol procedure AEs will be listed, and if the frequency of events allows, safety data will be summarized using descriptive methodology.

The incidence of symptoms for each treatment will be presented by severity and by association with investigational product as perceived by the investigator. Symptoms reported to occur prior to study entry will be distinguished from those reported as new or increased in severity during the study. Each symptom will be classified by the most suitable term from the medical regulatory dictionary.

The number of investigational product-related SAEs will be reported.

#### **10.3.1.2. Statistical Evaluation of Safety**

Safety parameters that will be assessed include safety laboratory parameters, CNS monitoring, eye assessments, vital signs, and ECG parameters. The parameters will be listed and summarized using standard descriptive statistics. Additional analyses will be performed if warranted upon review of the data. The statistical analysis plan will contain all details on the evaluation of safety measurements.

Analysis of QTc data from ECG monitoring in a Phase 1 trial is performed to judge the extent and/or risk of QT prolongation. A scatter plot will be generated to explore the relationship between QTc and drug exposure, and will assess the mean change in QTc using Fridericia's formula as a function of plasma drug concentration. The QTc analysis will not include ECGs collected in Part C (itraconazole interaction), due to the potential for non-LY3323795-induced changes in QTc.

Frequency tables of QTc changes from baseline and large QTc values may also be obtained in accordance with International Conference on Harmonisation guidance, and additional analyses may be conducted if required.

For each method of eye assessment, change from baseline (yes/no) and change from baseline clinically significant (yes/no) will be listed, and if there are sufficient changes they will be summarized by treatment group and compared with Fisher's exact test.

Additional analyses may be performed for the purpose of fulfilling the Clinical Trial Registry requirements.

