- Dose-dependent QT corrected for heart rate (QTc) prolongation occurred following repeated administration in dogs of doses at and above 5 mg/kg; peak changes at 5 mg/kg and 120 mg/kg were +7 msec and +31 msec, respectively. No qualitative electrocardiogram (ECG) abnormalities were observed. Decreases in heart rate also occurred following repeated administration in dogs of doses at and above 5 mg/kg; peak changes at 5 mg/kg and 120 mg/kg were -15 bpm and -39 bpm, respectively.
- In a single-dose cardiovascular safety study in dogs, QTc prolongation was noted at doses of 5 mg/kg ( $\leq +4$  msec) and 30 mg/kg ( $\leq +9$  msec). At all dose levels, minor decreases in heart rate were observed; at the 30-mg/kg dose level, a 6-bpm reduction in heart rate was observed (maximally). Also at the 30-mg/kg dose, minimally decreased systolic pressure (-7 mmHg), mean arterial pressure (-5 mmHg), and  $dP/dt_{max}$  (-240 mmHg/sec) occurred during the first 6 hours postdose.
- In rats, minimal increases in autofluorescent granules in the retinal pigmented epithelium were noted at the 150-mg/kg dose level and were considered nonadverse.
- The no-observed-adverse-effect level (NOAEL) of LY3323795 was 120 mg/kg in dogs and 150 mg/kg in rats.

Itraconazole, an antifungal agent, will be administered in Part C of this study as it is known to be a potent inhibitor of CYP3A, and is commonly used in drug interaction evaluations. Peak plasma concentrations of itraconazole are reached within 2 to 5 hours following oral administration. As a consequence of nonlinear PK, itraconazole accumulates in plasma during multiple dosing. Bioavailability is increased when itraconazole is administered with food. The terminal half-life of itraconazole generally ranges from 16 to 28 hours after single dose and increases to 34 to 42 hours with repeated dosing. Once treatment is stopped, itraconazole plasma concentrations decrease to an almost undetectable concentration within 7 to 14 days, depending on the dose and duration of treatment. The primary metabolite of itraconazole is hydroxy-itraconazole. Additional information including possible side effects of itraconazole can be found in the product insert.

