## 5.5. Justification for Dose

This study will evaluate plasma and CSF PK/PD of LY3323795 in an attempt to define a pharmaceutically relevant dose range for future studies. The initial proposed dose is 0.3 mg, which is anticipated to provide a maximum drug concentration ( $C_{max}$ ) of 0.625 ng/mL (90% confidence interval [CI]: 0.36, 1.11), and an area under the curve from time 0 extrapolated to infinity ( $AUC_{[0-\infty]}$ ) of 24.5 ng·hour/mL (90% CI: 9.09, 65.9). This dose (by body surface area) is substantially lower than the dose levels identified as the NOAELs in 1-month GLP toxicology studies and is therefore appropriate for use (Table SCAA.2). The doses (based on body surface area) identified as the NOAELs in rats and dogs are 4,500- and 12,000-fold greater than the starting dose in humans. Margins calculated based on AUC exposure at the NOAELs relative to predicted human exposures at 0.3 mg are  $\geq 1,408$ -fold (due to a gender difference in exposure) in rats and 2,214-fold higher in dogs.

In a cardiovascular safety pharmacology study in dogs, no changes in QTc prolongation occurred at a dose of 0.5 mg/kg; this dose (based on body surface area) is 63-fold higher than the proposed starting dose in Study SCAA of 0.3 mg.

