6.8.2.4. Vital Signs and Weight

Plot of vital signs and weight over time will be created for each patient.

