6.8.2.5. Electrocardiogram Intervals and Heart Rate

Analysis of corrected QT (QTc) data from ECG monitoring in a Phase 1 trial is performed to judge the extent and/or risk of QT prolongation. A scatter plot will be generated to explore the relationship between QTc and drug exposure, and will assess the mean change in QTc using

Fridericia's formula as a function of plasma drug concentration. The QTc analysis will not include ECGs collected in Part C (itraconazole interaction), due to the potential for non-LY3323795-induced changes in QTc. Frequency tables of QTc changes from baseline and large QTc values may also be obtained in accordance with International Conference on Harmonisation (ICH) guidance, and additional analyses may be conducted if required.

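### Heart rate is left out of the planned concentration-based cardiac analysis, although dogs showed heart-rate falls as well as QTc prolongation (low severity)

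*Protocol*

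**What the plan says.** Protocol 10.3.1.2 states: "A scatter plot will be generated to explore the relationship between QTc and drug exposure". It goes on to mean change in QTcF as a function of plasma concentration and excludes the Part C ECGs. SAP 6.8.2.5 repeats this. Its heading reads "6.8.2.5. Electrocardiogram Intervals and Heart Rate", but everything under that heading concerns QTc.

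Heart rate is covered elsewhere only descriptively. The protocol synopsis and 10.3.1.2 list and summarise ECG parameters and vital signs, which include pulse rate (protocol 9.4.2); the synopsis specifies values at each time point and changes from baseline. SAP 6.8.2.4 adds: "Plot of vital signs and weight over time will be created for each patient". Both documents allow further analyses if the data seem to warrant them.

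On the nonclinical side, protocol 3.2 says of the single-dose dog cardiovascular study: "At all dose levels, minor decreases in heart rate were observed". The largest fall was 6 bpm, at 30 mg/kg. QTc prolongation in that study was at most 4 msec at 5 mg/kg and at most 9 msec at 30 mg/kg. With repeated dosing, QTc prolongation and heart-rate decreases were both reported from 5 mg/kg upwards. For heart rate, "peak changes at 5 mg/kg and 120 mg/kg were -15 bpm and -39 bpm, respectively"; the QTc peaks at the same doses were +7 and +31 msec. Protocol 5.5 adds that in a dog cardiovascular study "no changes in QTc prolongation occurred at a dose of 0.5 mg/kg".

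**The concern.** The sponsor's own dog data contain two cardiac signals, and only one is carried into an analysis against exposure. The SAP heading suggests that heart rate was meant to be covered there. Protocol 10.3.1.2 leaves the details of safety evaluation to the SAP, so the gap is not filled elsewhere.

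Safety is the primary objective. Under the plan, a modest heart-rate effect would have to be noticed in summaries of 6 active subjects per dose level, read one time point at a time. In Part A the ECGs are triplicate and are taken at times that match PK samples, so the data for a better estimate are already being collected. Heart rate also helps in reading QTcF, because a heart-rate change moves QTcF slightly when the Fridericia exponent does not fit the subjects.

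**Working it through.** **1. The plan's own figure.** Table SCAA.2 gives a dog factor of 2400/120 = 20 and a human conversion of 52.9 mg/m² per 100 mg. So 0.5 mg/kg = 0.5 × 20 = 10 mg/m², and 0.3 mg = 0.3 × 0.529 = 0.1587 mg/m². The ratio is 10/0.1587 = 63.0, which reproduces the 63-fold in protocol 5.5. (The table's rounded 0.2 mg/m² would give 50.)

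**2. Where the dog doses fall on the human scale.** Each signal has to be placed on the same scale.

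| Dog dose | By body surface area | By Cmax |
|---|---|---|
| 0.5 mg/kg | 63 × 0.3 = 18.9 mg | 1018/10 = 101.8 ng/mL, assuming linearity; 101.8/210 × 100 = about 48 mg |
| 5 mg/kg | 100/52.9 × 100 = about 189 mg | 1018/210 = about 4.8 times the Cmax projected at 100 mg |

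The AUC limit of 3,450 ng·h/mL is projected to be met at 3,450/8,180 × 100 = about 42 mg.

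**3. Precision: inputs.**
- From the documents: 6 active and 3 placebo subjects at each of six Part A dose levels, so 6 × 3 = 18 placebo records if pooled; post-dose ECGs at 1, 2, 4, 6, 8, 12, 24 and 48 h; projected half-life 23 h; two-sided alpha 0.10 (SAP 6.1).
- Assumed, because the documents give none: SD of heart-rate change 3 to 5 bpm between and 4 to 6 bpm within subject-periods; a 5-bpm effect as benchmark; placebo records independent.

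**4. One time point.** Half-width = t(0.95, 22 df) × SD × √(1/6 + 1/18) = 1.717 × 0.4714 × SD = 0.809 × SD.
- Low SDs: √(3² + 4²) = 5.0, giving 4.05 bpm (4.047 before rounding).
- High SDs: √(5² + 6²) = 7.81, giving 6.32 bpm.
- Power for a 5-bpm fall: 66% and 37%.

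**5. Average of the 8 post-dose times.**
- Low SDs: √(9 + 16/8) = 3.32, giving 2.7 bpm.
- High SDs: √(25 + 36/8) = 5.43, giving 4.4 bpm.
- Power is 93% and 60% if the 5-bpm fall is sustained over all 8 times.

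**6. Concentration model.** Generalised least squares with known variances, placebo at zero concentration, a time effect and a subject-by-period effect. PK is one-compartment with a 23-h half-life, assumed absorption rate 0.7/h and assumed 30% between-subject exposure CV. The top dose is 100 mg, or 42 mg where the AUC limit is projected to be met. The half-width for the effect at the top-dose peak is about 2.1 to 3.8 bpm, and power is about 70 to 99%.

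**7. Where the gain comes from.** At a total SD of 5 bpm and a top dose of 100 mg, a concentration regression using one value per session has a half-width of 3.67 bpm, little better than 4.05. Using all 8 times with within-session correlation of 0.3 to 0.7 brings it to about 2.4 to 2.6. The repeated measures supply most of the improvement.

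Steps 5 and 6 do not estimate quite the same quantity. If the effect follows concentration, the PK assumptions in step 6 give relative levels of 0.57, 0.84, 1.00, 0.99, 0.95, 0.84, 0.59 and 0.29 at the 8 times. Their mean is 6.07/8 = 0.76 of peak. A simple average therefore dilutes a peak effect, and the model does not.

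**8. Effect on QTcF.** Shift = 410 × [(RR₂/RR₁)^(b − 1/3) − 1], with an assumed QTcF of 410 msec and a true exponent b of 0.30 to 0.38. A 5-bpm fall (65 to 60 bpm) gives −1.1 to +1.5 msec. A 10-bpm fall (65 to 55 bpm) gives −2.3 to +3.2 msec.

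**The case against.** The strongest reply is that heart rate is not neglected and that the nonclinical case for singling it out is thin. ECGs and vital signs are reviewed before every escalation (protocol 5.1.1.1), with the sponsor team unblinded (10.3.5). The plan has summaries, changes from baseline, individual plots and a clause for additional analyses. The single-dose dog falls were described as minor, and the larger falls followed repeated dosing, which this study does not use. The 6-bpm maximum came at 30 mg/kg: scaled linearly, 6 × 1018 = 6,108 ng/mL, about 28 times the median Cmax limit of 214 ng/mL. QTc itself gets only an exploratory plot. The precision figures rest on assumed SDs and an idealised model.

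Most of this stands and limits the severity. It does not close the gap: none of the planned displays estimates a heart-rate effect against exposure, and the additional-analyses clause commits to nothing specific.

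A reader might go further and infer that heart rate is the more sensitive signal, moving at a dose inside the human range while QTc does not. The documents do not support that. The repeat-dose studies give the same reported threshold for both. Protocol 3.2 names only 5 and 30 mg/kg for the single-dose study, so placing 0.5 mg/kg among its dose levels is an inference from 5.5. Setting about 19 mg for heart rate against about 5-fold for QTc mixes two scales. On one scale the contrast is 19 mg against 189 mg, or about 48 mg against about 4.8-fold, and 48 mg lies above the roughly 42 mg where the AUC limit is projected to be met.

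**Conclusion.** The point holds as a low-severity, exploratory gap. Heart rate, a signal reported in both dog studies and named in the SAP heading, has no concentration-based analysis, and the planned descriptive displays are imprecise. Under the assumed SDs, the half-width falls from about 4.0–6.3 bpm at one time point to 2.7–4.4 bpm for an average over the 8 times and about 2.1–3.8 bpm from the model. The model figures also require a roughly linear effect without delay. With larger SDs every approach is weaker: at a total SD of 10 bpm, power for 5 bpm is 27% at one time point and about 47 to 52% from a model with the top dose at 100 mg.

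A reader might also conclude that QTcF cannot be interpreted without heart rate. That is too strong: a 5-bpm fall shifts QTcF by only about −1.1 to +1.5 msec under the assumed exponents. Reading the two together is sensible practice, and the QTc analysis is not invalid without it.

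**What to change.** In protocol 10.3.1.2 and SAP 6.8.2.5, for Part A:

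- Add change in ECG heart rate (mean of each triplicate, from the same-period predose ECGs) as a second response, plotted and modelled against LY3323795 concentration.
- Set placebo records to zero concentration, since placebo samples are not planned for assay (protocol 9.5.1). Include a time effect and random effects for subject and subject-by-period.
- Report the estimate and 90% CI at the geometric mean Cmax of each dose.
- Check for delay between concentration and effect before relying on the linear model.
- Read the QTcF plot alongside the heart-rate result.

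Part A is the natural place: Part B has single ECGs at few times, and Part C is already excluded from the QTc analysis.

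The cost is wording in both documents and one extra exploratory plot and model. No visits, ECGs or samples are added. SAP 6.1 says that changes to the planned analysis do not require a protocol amendment, so the SAP text can be changed first. The downside is that the model assumes a roughly linear effect without delay, which a small study can check only loosely.

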### **10.3.2. Pharmacokinetic Analyses**

#### **10.3.2.1. Pharmacokinetic Parameter Estimation**

PK parameter estimates for LY3323795 will be calculated using standard noncompartmental methods of analysis.

The primary parameters for analysis will be  $C_{max}$  and AUC of LY3323795. Other noncompartmental parameters, such as half-life, apparent clearance, and apparent volume of distribution, may be reported.

Renal clearance of LY3323795 will be calculated as the ratio of amount excreted/AUC. This will be compared to the unbound glomerular filtration rate, which is estimated using creatinine levels.

In Part C, PK parameter estimates for itraconazole samples collected on Day 16 will be calculated using standard noncompartmental methods of analysis.  $C_{max}$  and AUC will be reported. Itraconazole concentrations collected as part of this study may be analyzed along with data collected in other studies as part of a larger assessment of itraconazole PK. If such an analysis is performed, the results of the analysis will be reported separately from the final report for this study. Concentrations of itraconazole metabolites may be characterized on an exploratory basis.

#### **10.3.2.2. Pharmacokinetic Statistical Inference**

In Part C, the  $AUC_{(0-\infty)}$  and  $C_{max}$  for LY3323795 administered alone and in the presence of itraconazole will be compared using an analysis of variance (ANOVA) model. The parameters will be log-transformed prior to analysis. The model includes a fixed effect for the treatment and a random effect for subject. The following model will be built:  $\ln(\text{PK parameter}) = \text{treatment} + \text{subject} + \text{random error}$  where treatment is a fixed effect with 2 levels: LY3323795 alone (reference) and LY3323795 with itraconazole (test).

The least square means for each treatment and the 90% CI for the difference in means will be estimated from the ANOVA model and back-transformed from the log scale to provide estimates of the geometric means and 90% CIs for the ratio of the geometric means of LY3323795 + itraconazole versus LY3323795 alone.

The time to  $C_{\max}$  ( $t_{\max}$ ) parameter will be analyzed using the Wilcoxon-signed rank test. Median differences and 90% CIs for the difference between LY3323795 + itraconazole (test) and LY3323795 alone (reference) will be calculated.

### 10.3.3. Pharmacodynamic Analyses

#### 10.3.3.1. Pharmacodynamic Parameter Estimation

In Parts A and B, plasma concentrations of  $A\beta_{1-40}$  and  $A\beta_{1-42}$  will be summarized for each dose group based on the  $C_{\text{nadir}}$  and the time to reach  $C_{\text{nadir}}$  ( $t_{\text{nadir}}$ ).

In Part B, CSF concentrations of  $A\beta_{1-40}$ ,  $A\beta_{1-42}$ , and CCI will be summarized for each dose group based on the  $C_{\text{nadir}}$ ,  $t_{\text{nadir}}$ , and the 24-hour average values, expressed as a percentage change from baseline. CCI

Other parameters may be calculated, as appropriate.

#### 10.3.3.2. Pharmacodynamic Statistical Inference

For Part B of this protocol, statistical analysis of CSF  $A\beta_{1-40}$  and  $A\beta_{1-42}$  concentrations obtained over the fixed-scheduled sampling period will be analyzed using a repeated-measures analysis with the primary statistical inference of pairwise comparison of the overall mean difference among the LY3323795 doses and placebo using a 90% CI. The statistical model may include the baseline CSF  $A\beta_{1-40}$  and  $A\beta_{1-42}$  concentrations obtained during predose CSF collection period and fixed effects of dose groups (placebo and doses of LY3323795), scheduled CSF sampling time, and the interaction between dose groups and sampling times. A compound symmetric covariance structure may be used. From the statistical model, the primary statistical estimates will be the mean percentage reduction from baseline in CSF  $A\beta_{1-40}$  and  $A\beta_{1-42}$  concentrations at each time point with LY3323795 over the 36-hour sampling interval. The above model will fit both the log-transformed and percentage change from baseline in CSF  $A\beta_{1-40}$  and  $A\beta_{1-42}$  concentrations.

CCI

### 10.3.4. Pharmacokinetic/Pharmacodynamic Analyses

It is intended that a compartmental modeling approach will be used to describe the plasma and CSF PK and CSF PD of LY3323795. Compartmental modeling will be performed using nonlinear mixed-effects modeling. Although it is not intended that the model will assess the impact of patient-specific factors (such as age, body weight, or race/subrace) on LY3323795 PK, these may be included if appropriate. Modeling may be performed sequentially by first modeling plasma PK and then fixing the values from that model when developing a model to describe CSF PK. It is intended that an indirect response model will be used to characterize the PD effect of LY3323795 on CSF  $A\beta_{1-40}$  formation, with PK parameters fixed to those values determined in previous steps. Other PD endpoints (eg,  $A\beta_{1-42}$ ) may be modeled, if warranted.

Other modeling approaches or graphical analyses may be used, as deemed appropriate. The results of this modeling may not necessarily be included in the final study report.

### **10.3.5. Interim Analyses**

No interim analyses are planned for this study. If an unplanned interim analysis is deemed necessary, the Lilly clinical pharmacologist, CRP/investigator, or designee will consult with the appropriate medical director or designee to determine if it is necessary to amend the protocol.

Safety and/or PK IAD reviews are scheduled to occur throughout the study. The purpose of these IAD reviews is to examine the safety data and guide dose selections.

In Part A, the investigator and the Lilly clinical pharmacologist/CRP/study team will make the determination regarding dose escalation based on their review of the safety and tolerability data, along with PK data, as applicable (Section 5.1.1).

In Part B, dose selection will be based on PK/PD data as described in Section 5.1.2.

The investigator will remain blinded and the Lilly clinical pharmacologist/CRP/study team will be unblinded during these IAD reviews.

The specifics about the timing of the IAD reviews and the procedures for selecting doses are described in the study design section of the protocol (Section 5).

Additional IAD reviews may be conducted at any time throughout the study as required to ensure subjects' safety or to help guide dosing. An assessment committee will not be formed.

## **Appendix 1. Abbreviations and Definitions**

---

Term	Definition
A<math>\beta</math>	$\beta$ -amyloid
AD	Alzheimer's disease
AE	adverse event: Any untoward medical occurrence in a subject or clinical investigation subject administered a pharmaceutical product that does not necessarily have a causal relationship with this treatment. An AE can therefore be any unfavorable and unintended sign (including an abnormal laboratory finding), symptom, or disease temporally associated with the use of a medicinal (investigational) product, whether or not related to the medicinal (investigational) product.
ALT	alanine aminotransferase
ANOVA	analysis of variance
APP	amyloid precursor protein
assent	Agreement from a child or other individual who is not legally capable of providing consent, but who can understand the circumstances and potential risks involved in participating in a study (required by some institutional review boards [IRBs]/ethical review boards [ERBs]).
AUC	area under the concentration-versus-time curve
AUC(0-<math>\infty</math>)	area under the curve from time 0 extrapolated to infinity
BACE	$\beta$ -site APP-cleaving enzyme
blinding	
A procedure in which 1 or more parties to the trial are kept unaware of the treatment assignment(s). Unless otherwise specified, blinding will remain in effect until final database lock.
 
A single-blind study is one in which the investigator and/or his staff are aware of the treatment but the subject is not, or vice versa, or when the sponsor is aware of the treatment but the investigator and/his staff and the subject are not. A double-blind study is one in which neither the subject nor any of the investigator or sponsor staff who are involved in the treatment or clinical evaluation of the subjects are aware of the treatment received.

BMI	body mass index
CI	confidence interval
Cmax	maximum drug concentration
Cnadir	nadir concentration
CNS	central nervous system
complaint	A complaint is any written, electronic, or oral communication that alleges deficiencies related to the identity, quality, purity, durability, reliability, safety or effectiveness, or performance of a drug or drug delivery system.

compliance	Adherence to all the trial-related requirements, good clinical practice (GCP) requirements, and the applicable regulatory requirements.
confirmation	A process used to confirm that laboratory test results meet the quality requirements defined by the laboratory generating the data and that Lilly is confident that results are accurate. Confirmation will either occur immediately after initial testing or will require that samples be held to be retested at some defined time point, depending on the steps required to obtain confirmed results.
CRF	case report form
CRP	clinical research physician: Individual responsible for the medical conduct of the study. Responsibilities of the CRP may be performed by a physician, clinical research scientist, global safety physician, or other medical officer.
CRU	clinical research unit
CSE	clinically significant event
CSF	cerebrospinal fluid
CYP	cytochrome P450
ECG	electrocardiogram
enroll	The act of assigning a subject to a treatment. Subjects who are enrolled in the trial are those who have been assigned to a treatment.
enter	Subjects entered into a trial are those who sign the informed consent form directly or through their legally acceptable representatives.
ERB	ethical review board
GLP	good laboratory practice
HIV	human immunodeficiency virus
IAD	interim access to data
IB	Investigator's Brochure
ICF	informed consent form
ICH	International Conference on Harmonization
informed consent	A process by which a subject voluntarily confirms his or her willingness to participate in a particular trial, after having been informed of all aspects of the trial that are relevant to the subject's decision to participate. Informed consent is documented by means of a written, signed, and dated informed consent form.
interim analysis	An interim analysis is an analysis of clinical trial data, separated into treatment groups, that is conducted before the final reporting database is created/locked.

Investigational New Drug	An application to the FDA to allow testing of a new drug in humans.
investigational product	A pharmaceutical form of an active ingredient or placebo being tested or used as a reference in a clinical trial, including products already on the market when used or assembled (formulated or packaged) in a way different from the authorized form, or marketed products used for an unauthorized indication, or marketed products used to gain further information about the authorized form.
investigator	A person responsible for the conduct of the clinical trial at a trial site. If a trial is conducted by a team of individuals at a trial site, the investigator is the responsible leader of the team and may be called the principal investigator.
IRB	institutional review board
LC/MS/MS	liquid chromatography with tandem mass spectrometry
Legal Representative	An individual or judicial or other body authorized under applicable law to consent, on behalf of a prospective subject, to the subject's participation in the clinical trial.
LP	lumbar puncture
MTD	maximum tolerated dose
NOAEL	no-observed-adverse-effect level
non-investigational product	A product that is not being tested or used as a reference in the clinical trial, but is provided to subjects and used in accordance with the protocol, such as: concomitant or rescue/escape medication for preventative, diagnostic, or therapeutic reasons, medication to ensure adequate medical care, and/or products used to induce a physiological response.
open-label	A study in which there are no restrictions on knowledge of treatment allocation, therefore the investigator and the study participant are aware of the drug therapy received during the study.
PK/PD	pharmacokinetic(s)/pharmacodynamic(s)
QTc	QT corrected for heart rate
RDA	recommended dietary allowance
SAE	serious adverse event
CCI	
screen	The act of determining if an individual meets minimum requirements to become part of a pool of potential candidates for participation in a clinical trial.
SUSAR	suspected unexpected serious adverse reaction
tmax	time to C max

CCI

tnadir	time to reach C nadir
treatment-emergent adverse event	Any untoward medical occurrence that emerges during a defined treatment period, having been absent pretreatment, or worsens relative to the pretreatment state, and does not necessarily have to have a causal relationship with this treatment
ULN	upper limit of normal

---

